8.1 Primary analysis

The primary analysis will be to examine the sleep quality (SQ) component score of the SF-B total for a significant change between the app and the control condition at baseline (week 0), at 6 weeks, and at 12 weeks.

8.2 Secondary analyses

The sleep quality SQ component of the SF-B will be calculated similar to the primary analysis, but using a per-protocol approach (participants who are adherent to treatment), excluding participants who did not sufficiently engage with app throughout the study (<3 tracked nights of sleep per week, as averaged over the entire follow-up period, respectively used the app modules regularly).

The GES component of the SF-B (feeling of being refreshed after sleep), the physiological and psychological component of the SF-12, the total score of the Pittsburgh Sleep Quality Index questionnaire (PSQI) and the score of the perceived stress scale PSS will be tested for significant changes between app condition and control condition at baseline, at 6 weeks and at 12 weeks. This will be done with the paired t-test, if there are no significant deviations from a normal distribution, otherwise the Wilcoxon matched pairs test will be used.

Objective sleep parameters (sleep onset latency, wake after sleep onset, total sleep time, sleep efficiency, sleep stages, nighttime awakenings) will be tested for significant change in the app condition comparing baseline with data at 6 and 12 weeks of follow-up.

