1. Start the sleep tracking device via a smartphone app before lying down in bed and turning off the lights to go to sleep (only for intervention (app) group).
2. In the morning, turn off the sleep tracking device as soon as they wake up and decide to leave the bed (only for intervention (app) group).
3. Log day and regularly use the different modules addressing different aspects of sleep, including advice for change (only for intervention (app) group).
4. At the three time points shown in 8.4.1 flow diagram, complete a longer questionnaire using an E-Link. These questionnaires will cover demographic information, subjective mental and physical health, subjective sleep, and stress level. (valid for app condition and waitlist control group)

8. Intensity of Use

Although app condition participants will be instructed to track sleep and engage with the app every night, the minimal internal compliance threshold for intensity of use is set at 3 nights of tracking per week. If participants track less than 3 nights per week, they will receive up to 3 reminder follow-up emails. The primary analysis will include all randomized participants. Secondary analyses will be conducted using an adherent to treatment approach, excluding participants who did not sufficiently engage with app throughout the study (<3 tracked nights of sleep per week).

9. Research methods

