9.8 Data analysis

Demographic and other key study variables will be compared between intervention group and control group at the baseline using t tests for continuous variables and chi squared for categorical variables to test whether the randomization has worked adequately.

The primary analysis will include all randomized participants. Secondary analyses will be conducted using an adherent to treatment approach, excluding participants who did not sufficiently engage with app throughout the study (<3 tracked nights of sleep per week, respectively used the app modules regularly).

The questionnaire data will be analyzed by an ANOVA, with one factor (app condition vs. waitlist control group) and time (Baseline, 6-weeks, 12-weeks). To handle missing values, a mixed-model approach with the same factors will be applied. The critical statistical test would be the interaction term between app condition and the waitlist control group.

For objectively recorded sleep data, repeated measured data will be analyzed using multi-level modeling (MLM) in a nested way (nights within participants), will be performed allowing for analyzing changes with the intervention (app) group. To evaluate changes in primary and secondary outcome measures assessed by validated scales at baseline, 6-weeks, and 12-weeks, we will compare within-group differences for each time-point using a t-test if normally distributed, or the Mann Whitney-U test for non-normally distributed continuous data. In addition, effect sizes for the changes within both groups (questionnaire data) and app group (objective sleep parameters) will be computed.

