4.1 Definitions

“App condition”: Participants randomized to tracking their sleep with the Dein Schlaf. Dein Tag. application.
“Waitlist condition” (control condition): Participants randomized to a waitlist group without using the application.

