4.3 Violations of the protocol

Participants in the app condition who do not track their sleep for 3 nights or more per week will be excluded from parts of the secondary analyses.

5 Variables

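### SAP 8.2 repeats the sleep-quality comparison after dropping low-use participants from the app arm only, so this secondary efficacy estimate is not a randomised comparison

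*SAP*

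**What the plan says.** SAP 8.2 specifies a further analysis of SQ "using a per-protocol approach (participants who are adherent to treatment), excluding participants who did not sufficiently engage with app throughout the study". Apart from that exclusion, the score "will be calculated similar to the primary analysis". The primary analysis in SAP 8.1 examines SQ "for a significant change between the app and the control condition" at weeks 0, 6 and 12, so the per-protocol version is also a between-arm comparison.

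The arm affected is named in SAP 4.3: "Participants in the app condition who do not track their sleep for 3 nights or more per week will be excluded". This covers some secondary analyses only. SAP 4.1 defines the waitlist as "Participants randomized to a waitlist group without using the application".

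The tracking threshold is three nights per week in Protocol 8 and 9.8 and in SAP 4.3 and 8.2. SAP 8.2 adds how it is computed: "as averaged over the entire follow-up period". Protocol 9.8 and SAP 8.2 both append a second criterion, "respectively used the app modules regularly", without a number. SAP 5.3 and 8.4 list time spent on the guide as a measure of interaction, also without a cut-off.

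Protocol 8 and 9.8 keep every randomised participant in the primary analysis, and Protocol 9.4.5 calls the final analysis intention to treat.

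**The concern.** Randomisation makes the two whole arms comparable. It does not make adherent app users comparable with a waitlist that still contains the people who would not have adhered. The waitlist counterparts of the excluded app users cannot be identified, because adherence is observed in one arm only.

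The planned group-by-time test (SAP 7) removes stable baseline differences. It does not remove a link between adherence and change in SQ. Such a link is plausible, although the documents do not show one: allocation is known to participants and SQ is self-reported. If people who feel no benefit stop tracking, the bias favours the app. If people whose sleep has improved stop tracking, it goes against the app.

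This is an efficacy estimate on the primary outcome, listed first in SAP 8.2, with no adjustment, no caveat and no randomisation-based estimate of the effect in adherers beside it. The module-use clause also leaves the analysis set open. Its connective does not say whether the two criteria are joined by and or by or. Read literally inside the exclusion bracket, it would remove regular module users.

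**Working it through.** **Which participants are compared.** Taken alone, SAP 8.2 could be read as excluding anyone with too few tracked nights. That would empty the waitlist, which has none. SAP 4.3 settles it: the exclusion acts on the app condition. With SAP 8.1 and 4.1, the comparison is adherent app users against the whole waitlist.

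**Size of the bias.** The plan gives no figure for this, so there is nothing to reproduce. Inputs:

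- Randomised per arm: n = 300 (Protocol 9.6). I also use n = 150, the number per group that Protocol 9.6 gives before its increase for dropout.
- Adherent share p: assumed 0.6 or 0.8.
- Correlation r between tendency to adhere and change in SQ: assumed 0 to 0.3.
- True effect zero, outcomes complete, two-sided 5% test, unit = SD of change in SQ.

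For a normal adherence tendency cut so that a share p adheres, the mean change among adherers is shifted by

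bias = r × φ(z)/p, with z = Φ⁻¹(1 − p).

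- p = 0.6: φ(z)/p = 0.644, so r = 0.1/0.2/0.3 gives 0.064/0.129/0.193 SD.
- p = 0.8: φ(z)/p = 0.350, giving 0.035/0.070/0.105 SD.

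The standard error is SE = √(1/(np) + 1/n), and the rejection probability is Φ(b/SE − 1.96) + Φ(−b/SE − 1.96), where b is the bias.

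| n per arm | p | Compared | SE | r = 0 | r = 0.1 | r = 0.2 | r = 0.3 |
|---|---|---|---|---|---|---|---|
| 300 | 0.6 | 180 v 300 | 0.094 | 5% | 10.5% | 27.7% | 53.5% |
| 300 | 0.8 | 240 v 300 | 0.087 | 5% | 6.9% | 12.8% | 22.8% |
| 150 | 0.6 | 90 v 150 | 0.133 | 5% | 7.7% | 16.2% | 30.5% |
| 150 | 0.8 | 120 v 150 | 0.122 | 5% | 5.9% | 8.8% | 13.7% |

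Negative r gives the same rejection rates with the bias against the app.

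**Does the planned test change this?** Assume the same bias at weeks 6 and 12 and a correlation ρ between the two changes. The 2-df group-by-time test then has noncentrality 2(b/SE)²/(1 + ρ). For n = 300, p = 0.6 and r = 0.1/0.2/0.3, rejection is 10.0/27.2/55.3% at ρ = 0.5 and 9.4/24.4/49.8% at ρ = 0.7. The picture is essentially the same.

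**What a complier-average estimate would cost and risk** (p = 0.6):

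- Precision: SE = √(2/n)/p = 0.136 for n = 300, against 0.094 above; 0.192 for n = 150, against 0.133.
- Exclusion failure: if below-threshold use has an effect e, the estimate is too high by e(1 − p)/p. For e = 0.10 SD this is 0.10 × 0.4/0.6 = 0.067 SD; at p = 0.8 it is 0.025 SD.
- Dropout in app non-adherers only: suppose 10/50/10% are missing in app adherers, app non-adherers and waitlist. The observed app arm is then 0.54 + 0.20 = 0.74 of those randomised, with mean change (0.54 × 0.644r − 0.20 × 0.966r)/0.74 = 0.209r. The observed adherent share is 0.54/0.74 = 0.730. The unweighted estimate is biased by 0.209r/0.730 = 0.286r, or 0.057 and 0.086 SD at r = 0.2 and 0.3. Inverse-probability weighting removes this.
- Equal dropout in both arms (10/50%): the unweighted bias cancels, but weighting that cannot see would-be adherence on the waitlist gives −0.209r/0.6 = −0.348r, or −0.070 and −0.104 SD.

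**The case against.** The plan already contains the problem. The primary analysis keeps all randomised participants, SAP 8.2 labels this analysis secondary and per-protocol, and no section ties a success claim to it. Any per-protocol set defined by use of an app that only one arm has will produce this comparison. All of that stands, and it limits the weight of the point. It does not supply the missing caveat or make the estimate unbiased.

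The size is unknown. Neither r nor the adherent share is in the documents, and r may be zero or negative. The payment for regular use (Protocol 9.4.7) and the reminders ("If participants track less than 3 nights per week, they will receive up to 3 reminder follow-up emails", Protocol 8) may weaken the link. At 80% adherent and 150 per arm, the inflation is only to 6–14% for r = 0.1–0.3. This also stands, which is why the full range is shown.

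A complier-average estimate has weaknesses of its own. Its exclusion assumption is doubtful, because the advice and prompts described in Protocol 9.4.9 also reach people who track little. It is imprecise: for an effect of 0.20 SD in adherers, power is about 31% at SE 0.136. That is reason to report it beside the table with its assumptions stated, and to keep the weighted version as a sensitivity analysis.

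A reader might infer that the documents conflict on whether the threshold must be met on average or in every week. They do not. SAP 8.2 states averaging, the other sections are silent, and none requires the threshold in each week. Only the module-use clause is undefined.

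**Conclusion.** The per-protocol SQ analysis in SAP 8.2 is a non-randomised comparison and should not be read as an efficacy estimate without that label. It is unbiased only if adherence is unrelated to change in SQ. Under the assumptions above, the bias for r = 0.1–0.3 is 0.04–0.19 SD of change in absolute size. The false-positive rate rises from 5% to between 6% and 54%, depending on r, adherent share and numbers analysed.

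Two stronger readings are not supported. A reader might infer that the trial's main result is compromised; it is not, because the primary analysis includes everyone randomised. A reader might also infer that the analysis is tilted in favour of the app; the documents do not give the direction, and it could go either way. The point is a worthwhile correction to a secondary analysis, and the undefined module-use clause should be settled with it.

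**What to change.** 1. Keep the adherers-versus-waitlist table only as a labelled non-randomised, exploratory analysis, and draw no efficacy claim from it.

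2. Report beside it a complier-average effect on SQ at weeks 6 and 12: two-stage least squares, allocation as instrument, baseline SQ as covariate. Use one binary exposure throughout: a mean of at least three tracked nights per week over the entire follow-up, as in SAP 8.2, with the waitlist set to 0. State the exclusion assumption that below-threshold use has no effect, and say why it is doubtful. Give an inverse-probability-weighted version only as a sensitivity analysis for dropout. Nothing is imputed, so this is consistent with SAP 6.1.

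3. Delete the module-use clause ("respectively used the app modules regularly") from Protocol 9.8 and SAP 8.2, or give it a numeric cut-off and an explicit and/or.

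Items 1 and 3 cost only wording. Item 2 needs an extra model at two visits plus a missingness model for the sensitivity analysis, using the nightly usage log already described in SAP 8.4. Its price is wider intervals (SE about 0.136 against 0.094 SD at 60% adherent and 300 per arm; 0.192 with 150 per arm) and sensitivity to differential dropout. It adds no evidence against the null beyond the all-randomised test. A whole-follow-up exposure also classifies people at week 6 partly by later use, which makes the exclusion assumption weaker at that visit.

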9.4.3 Secondary Endpoints

Improvements in sleep metrics between app condition and waitlist condition comparing baseline with 6 weeks and 12 weeks measures

Note, given the dynamic and personalized nature of the intervention and its potential impact on various self-assessed goals, we have chosen multiple secondary endpoints that we expect to see statistically significant sleep improvements in depending on baseline self-reported sleep parameters, including the following:

- Health measures including overall sleep problems, feeling of being refreshed in the morning, mental health stress (PSQI, PSS, SF-12, SF-B)
- Objective sleep parameters (only app condition): Total sleep time, sleep onset latency, wake after sleep onset, sleep efficiency.
- Self-reported app-based items in app condition group.

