9.6 Study size

An a priori power analysis was performed using GPower version 3.1.9.7. Previous research indicates that effect sizes between 0.20 and 0.50 can be expected using a digital sleep application. A conservative approach (assuming an effect size of 0.20) will require 150 participants in each group (N=150) to detect significant effects between app group and wait-list control group for both primary and secondary outcome measures (alpha: 0.05, power: 0.80, allocation ratio 1:1). As trials with solely online recruitment may have higher drop out rates, we increased the participants in each group to 300 (total: 600 participants).

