8.5 Subgroup analyses and analyses of further secondary parameters

Further secondary parameters might be tested for differences between app group and control group at week 0, week 6 and week 12: Components of the SF-B: mental comfort before sleep (PSYA), mental weariness before sleep (PSYE), psychosomatic symptoms during sleep (PSS), dream memory (TRME), difficulties falling asleep (ESS), difficulties staying asleep (DSS), early awakening (VZA) and general sleep characterisation (ASC).

9 Software

SAS (SAS Institute) will be the main statistical programming software.

10 Appendices – Tables, Lists, Figures

[figure not shown]
10.1 Tables:

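### Secondary significance tests (five questionnaire scores, six objective parameters, eight optional SF-B components) have no gate, order, adjusted level or exploratory label

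*SAP*

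**What the plan says.** Protocol 9.4.3 frames the secondary endpoints in terms of significance: "we have chosen multiple secondary endpoints that we expect to see statistically significant sleep improvements in". SAP 8.2 takes five questionnaire scores: "The GES component of the SF-B (feeling of being refreshed after sleep), the physiological and psychological component of the SF-12", the PSQI total and the PSS. It says that they "will be tested for significant changes between app condition and control condition at baseline, at 6 weeks and at 12 weeks", by a paired t-test or its rank-based counterpart. The same section tests six objective parameters for significant change from baseline at 6 and 12 weeks, in the app arm only.

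SAP 8.5 adds eight SF-B components on an optional basis: "Further secondary parameters might be tested for differences between app group and control group at week 0, week 6 and week 12".

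The SAP gives no significance level. The only one in either document is in Protocol 9.6 ("alpha: 0.05, power: 0.80, allocation ratio 1:1"), where the sample size is meant "to detect significant effects between app group and wait-list control group for both primary and secondary outcome measures". For questionnaire data, SAP 7 makes one group-by-time interaction the critical test. SAP Annex II (10.3.2) assigns responsibility for p-values on both the questionnaire and the app data.

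**The concern.** A plan that looks for significance on many secondary measures needs a rule for which results may be claimed. None is given, so after a null or borderline result on SQ any secondary p-value below 0.05 could be presented as an improvement.

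SAP 8.5 is the weakest place, for two reasons. By SAP 5.2, four of the eight components (ESS, DSS, VZA, ASC) are building blocks of SQ. Because testing them is optional, the pieces of a failed primary score could be examined and only the favourable ones shown. Second, the week-0 tests can say nothing about the app: SAP 4.2 places the baseline assessment before randomisation, so any difference between arms there is chance.

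The set of secondary endpoints also varies between places. Protocol section 7 names three objective parameters, 9.4.3 four, the abstract five, and the cover page and SAP six. The self-reported app items in Protocol 9.4.3 have no analysis in the SAP.

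**Working it through.** **Figures in the plan.** The documents state no familywise error rate, so there is none to reproduce. The one related figure, 150 per group for an effect size of 0.20, does not follow if 0.20 is read as a standardised mean difference (the metric is not stated): 2 × (1.960 + 0.842)² / 0.20² = 392.5, or 393 per group, two-sided. The error rates below do not depend on this figure.

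**Inputs from the documents.** Five scores and six objective parameters (SAP 8.2); eight optional components (SAP 8.5); two follow-up visits; level 0.05 (Protocol 9.6), taken as two-sided because sidedness is not stated. The full count is (5 + 8 + 6) × 2 = 38 tests. It treats sleep staging as one variable and leaves out the week-0 and within-arm tests.

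**Assumptions not in the documents.** Correlation between scores 0 to 0.6; between visits 0.5; questionnaire and objective blocks independent of each other; no true effect and no drift over time.

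**Step 1: independent tests.** The chance of at least one p<0.05 is 1 − 0.95^k.
- k = 5: 22.6%
- k = 10: 40.1%
- k = 16: 56.0%
- k = 38: 85.8%

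**Step 2: correlated tests.** Simulation of 200,000 sets of correlated normal test statistics with critical value 1.960. The lower end of each range is at score correlation 0.6, the upper end at 0.

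| Family | Tests | Either direction | In the app's favour |
|---|---|---|---|
| Five scores, one test each | 5 | 17-23% | 8-12% |
| Five scores, weeks 6 and 12 | 10 | 29-38% | 14-21% |
| Eight components, weeks 6 and 12 | 16 | 37-53% | 19-31% |
| All 19 measures, two visits | 38 | 63-84% (0.635 to 0.836) | 36-59% (0.359 to 0.587) |

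The first row corresponds to the single interaction test of SAP 7, the second to testing at each follow-up visit as SAP 8.2 can be read. With three time points the interaction has two degrees of freedom and its p-value carries no direction, so the first row treats each test as a single contrast.

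**Step 3: what a gate and Holm do.** If a secondary claim requires a significant SQ test, and the app does not affect SQ, the chance of any secondary claim cannot exceed the primary test's 5%. If SQ does respond, Holm keeps the chance of a false claim among the five scores at or below 5%. Its strictest step is 0.05 / 5 = 0.01.

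**Step 4: power cost.** An effect with 80% power at 5% has Φ(1.960 + 0.842 − 2.576) = Φ(0.226) = 59% at 1%. For a standardised difference of 0.20 (assumed metric), the expected z is 0.20 × √(n/2).
- 300 per arm: z = 2.449; power falls from 69% to 45%.
- 150 per arm: z = 1.732; power falls from 41% to 20%.

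The gate lowers these further, by an amount that depends on the unknown correlation with SQ.

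**The case against.** SQ is plainly the single primary variable (Protocol 9.4.2, SAP 5.2 and 8.1), and everything else is called secondary or further secondary. Many readers would treat unadjusted secondary p-values as supportive without being told. Protocol 9.4.3 states an expectation and not a rule for claims. All eight components are named in advance, and within the SAP the six objective parameters are the same in 3.1, 5.3 and 8.2. On the reading in SAP 7 there is one test per score, which gives the lowest row of the table, and only errors in the app's favour can become claims of benefit.

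Much of this stands, and it limits the size of the point. It does not supply the missing rule: naming components in advance does not prevent selection when testing them is optional, and secondary is not the same as exploratory when significance is the stated aim.

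A reader might go further and infer that all 19 measures are tested at 5%, so that a false secondary claim is likely even if the app does nothing. The documents do not support that:
- The 0.05 level for secondary tests is inferred from Protocol 9.6, and the eight components may never be tested.
- For the five planned scores the chance is 17-38% in either direction and 8-21% in the app's favour.
- It passes one half in the app's favour only for the full 38 tests with scores close to uncorrelated.
- A week-0 difference cannot be reported as an app effect and should not be counted.
- The objective tests are before-after comparisons without a control. Drift or regression to the mean, in a group selected on a Regensburg score of 13-24, could make them significant whatever the level, so an alpha adjustment would not cure them.

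**Conclusion.** The point holds as a gap in claim rules and deserves a change, but it does not touch the error rate of the primary test. On the assumed correlations, the chance of at least one false positive among the five planned scores is about three to eight times the nominal 5% in either direction (17% / 5% = 3.4; 38% / 5% = 7.6). The 63-84% for the full list is a ceiling that applies only if every optional and objective test is run at both visits and the two blocks are independent.

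Which row applies to the five scores cannot be settled from the documents: SAP 7 points to one interaction test per score, while SAP 8.2 names paired tests, which do not compare two separate arms. The clearest defect needs no simulation: optional tests on parts of the primary score, with no duty to report them all.

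**What to change.** 1. **SAP 8.5.** Replace the permissive wording with a commitment that all eight components will be reported as between-arm estimates with 95% confidence intervals, labelled exploratory. Delete the week-0 tests.
2. **SAP 8.2, five questionnaire scores.** Allow significance claims only if the primary SQ test is significant. For each score use the group-by-time interaction that SAP 7 makes critical, in place of the paired tests, with Holm at 5% across the five. If SQ is not significant, report estimates and 95% confidence intervals, labelled exploratory.
3. **SAP 7 and 8.2, remaining analyses.** Report the objective parameters as uncontrolled app-arm estimates, and within-arm questionnaire changes as descriptive estimates, both with confidence intervals. Report the per-protocol SQ result as a supportive estimate with a confidence interval.
4. **Protocol and SAP.** Use one list of secondary endpoints throughout, and either give the self-reported app items an analysis or remove them from the list.

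Cost: no new data. Each secondary claim loses power, from 80% to 59% at the strictest Holm step and lower again with the gate. The gate and the all-or-none reporting of components give most of the protection; the Holm step is the more debatable part. Items 1 to 3 need SAP wording, but SAP 7 repeats Protocol 9.8, so that section should be kept in line. Item 4 needs a protocol amendment, which Protocol 9.4 sends to the Ethics Committee before implementation.

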9.1 Study design

The study is a randomized waitlist controlled trial of a sleep improvement app. The present study design is summarized in Figure 1. We decided to use a between-group design as we want to determine the effect of the sleep improvement app vs. not using anything, as the study app is aiming to improve subjective sleep quality in order to prevent progression to clinical relevant sleep problems (primary prevention). Participants will be randomly assigned to the Sleep Improvement App intervention or the waitlist condition. Online assessments will take place at Baseline (0 weeks), 6 weeks (during the intervention), and 12 weeks (after intervention).

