9.2 Randomization and allocation concealment

This study will use simple randomization with an allocation ratio of 1:1, as recommended for large randomized controlled trials. Randomization will be conducted by an automated online system; hence the research team will be unable to influence randomization and have no access to future allocations.

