3.1 Objectives and aims

Primary outcome

- Changes in score of the sleep quality (SQ) component of the SF-B comparing app and waitlist condition at baseline with data at 6 and 12 weeks of follow-up.

Secondary outcomes

Changes in subjective sleep parameters (questionnaires) comparing app and waitlist condition at baseline with data at 6 and 12 weeks of follow-up.

- Changes in scores of the “feeling refreshed after sleep” (GES) component of the SF-B
- Changes in physiological and psychological component scores of the SF-12
- Changes in quality of sleep (QoS), measured by the Pittsburgh Sleep Quality Index (PSQI) total score
- Changes in scores of the perceived stress scale (PSS)

Changes in objective sleep parameters in the app condition at baseline with data at 6 and 12 weeks of follow-up.

- Changes in sleep onset latency
- Changes in wake after sleep onset time
- Changes in total sleep time
- Changes in sleep efficiency
- Changes in sleep staging
- Changes in nighttime awakenings

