6.2 Outliers

The analyses comprise all measured and documented values. Excluded are only those values that have been identified or confirmed by an investigator to be a measurement error or a confirmed false entry, e.g. typos in the date of birth.

7 Statistical methods

Demographic and other key study variables will be compared between intervention group and control group at the baseline using t tests for continuous variables and chi squared for categorical variables to test whether the randomization has worked adequately.

The questionnaire data will be analyzed by an ANOVA, with one factor (app condition vs. waitlist control group) and time (Baseline, 6-weeks, 12-weeks). To handle missing values, a mixed-model approach with the same factors will be applied. The critical statistical test would be the interaction term between app condition and the waitlist control group.

For objectively recorded sleep data, repeated measured data will be analyzed using multi-level modeling (MLM) in a nested way (nights within participants), will be performed allowing for analyzing changes with the intervention (app) group. To evaluate changes in primary and secondary outcome measures assessed by validated scales at baseline, 6-weeks, and 12-weeks, we will compare within-group differences for each time-point using a t-test if normally distributed, or the Mann Whitney-U test for non-normally distributed continuous data. In addition, effect sizes for the changes within both groups (questionnaire data) and app group (objective sleep parameters) will be computed.

8 Statistical analyses

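### SAP 8.2 assigns paired tests to the app-versus-waitlist comparison of five secondary scores, which they cannot make, and so conflicts with the interaction test in SAP 7 and protocol 9.8

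*SAP*

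**What the plan says.** The secondary questionnaire objective is a between-arm one. Protocol 9.4.3 gives it as "Improvements in sleep metrics between app condition and waitlist condition comparing baseline with 6 weeks and 12 weeks measures", and SAP 3.1 as "Changes in subjective sleep parameters (questionnaires) comparing app and waitlist condition at baseline with data at 6 and 12 weeks of follow-up".

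SAP 8.2 takes five scores (SF-B GES, the physiological and psychological SF-12 components, PSQI total, PSS) and says they "will be tested for significant changes between app condition and control condition at baseline, at 6 weeks and at 12 weeks". The next sentence names the method: "This will be done with the paired t-test, if there are no significant deviations from a normal distribution, otherwise the Wilcoxon matched pairs test".

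SAP 7 and protocol 9.8 treat all questionnaire data differently. They specify an ANOVA with group and time (baseline, 6 and 12 weeks), with a mixed model on the same factors to deal with missing values, and add: "The critical statistical test would be the interaction term between app condition and the waitlist control group". App and waitlist are two levels of one factor, so the only interaction available is group by time.

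On the design, protocol 9.1 says "Participants will be randomly assigned to the Sleep Improvement App intervention or the waitlist condition" and protocol 9.2 says "This study will use simple randomization with an allocation ratio of 1:1".

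**The concern.** A paired test needs two linked measurements per unit. Here the link exists only between visits of the same participant; no app participant is matched to a waitlist participant. The tests named in 8.2 can therefore show whether one arm changed, but not whether the arms changed by different amounts.

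8.2 is the only section that assigns a test to these five scores by name, so an analyst could reasonably follow it in preference to the general text in SAP 7. The control arm would then play no part in inference on five secondary endpoints, and a change common to both arms could be presented as an app effect. With two written methods and no order between them, the choice could also be made after results are seen.

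A smaller, separate slip: for within-group change, SAP 7 and protocol 9.8 name the Mann-Whitney U test, which is for independent samples, and do not say that the t-test is paired.

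**Working it through.** **1. The texts side by side.**

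| Place | Comparison | Test named |
|---|---|---|
| Protocol 9.4.3, SAP 3.1 | app vs waitlist, change from baseline | none |
| Protocol 9.8, SAP 7 | questionnaire data, group and time | interaction in ANOVA or mixed model |
| Protocol 9.8, SAP 7 (supplementary) | change within each group | t-test or Mann-Whitney U |
| SAP 8.1 (primary SQ) | app vs waitlist | none, so SAP 7 applies |
| SAP 8.2 (five scores) | app vs waitlist | paired t-test or Wilcoxon matched pairs |

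SAP 8.2 is the outlier. SAP 6.1 refers the reader to sections 7 and 8 together and ranks neither.

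**2. Could app and waitlist participants be paired?** No pairing is defined. Nor would the arms usually be the same size: if exactly 600 are simply randomised, P(300 in each arm) = C(600,300)/2^600 = 0.0326. The tests must therefore be run within an arm.

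**3. What within-arm tests show when the app does nothing.** The plan has no figure of its own to reproduce here. Assumptions not in the documents: no app effect; the same drift g (in SD units) in both arms; baseline to follow-up correlation r of 0.3 to 0.7; 150 to 300 analysed per arm (the two group sizes in protocol 9.6); two-sided 0.05.

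The SD of change is √(2(1−r)) and the noncentrality is g√n/√(2(1−r)). Example: with r = 0.5 the SD of change is 1. For g = 0.2 and n = 150 the noncentrality is 0.2 × √150 = 2.45, and the noncentral t gives p = 0.682.

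Probability p that the app-arm paired test is significant, with p(1−p) in brackets (app significant, waitlist not):

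| n per arm | r | g = 0.1 | g = 0.2 | g = 0.3 |
|---|---|---|---|---|
| 150 | 0.3 | 0.177 (0.146) | 0.539 (0.249) | 0.870 (0.113) |
| 150 | 0.5 | 0.230 (0.177) | 0.682 (0.217) | 0.955 (0.043) |
| 150 | 0.7 | 0.349 (0.227) | 0.881 (0.105) | 0.997 (0.003) |
| 300 | 0.3 | 0.309 (0.213) | 0.831 (0.140) | 0.992 (0.008) |
| 300 | 0.5 | 0.408 (0.242) | 0.932 (0.063) | 0.999 (0.001) |
| 300 | 0.7 | 0.606 (0.239) | 0.994 (0.006) | 1.000 (0.000) |

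A between-arm t-test of change, which is the interaction contrast for two time points, was simulated with 10,000 trials per setting and drift of 0 to 0.3 SD. It rejected in 4.5% to 5.6%. A separate run at r = 0.5 with 20,000 trials gave 4.8% to 5.2%.

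**4. The Mann-Whitney slip.** With no true change, Mann-Whitney applied to the two visits of one arm ignores the correlation. Simulated rejection was 0% to 2.1% instead of 5%, over r = 0.3 to 0.7 and normal, lognormal and bounded skewed data. An unpaired t-test rejects in 2(1 − Φ(1.96/√(1−r))) = 1.9%, 0.56% and 0.03% at r = 0.3, 0.5 and 0.7. The signed-rank test gave 4.1% to 5.5% (normal and lognormal data).

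**The case against.** The best defence is that the between-arm test already exists. SAP 7 and protocol 9.8 put all questionnaire data into the group and time model without exception, all five scores are questionnaire data, and 8.2 does not say that it replaces that model. On this view 8.2 is a misplaced description of the supplementary within-group tests in SAP 7: it has the same structure (normality check, t-test, rank alternative), and the tests it names are valid for within-arm change. SAP 7 also asks for "effect sizes for the changes within both groups (questionnaire data"), so drift on the waitlist would be visible.

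Part of this stands. The plan as a whole does contain a valid test, and the harm arises only if 8.2 is followed on its own. The percentages above are probabilities of correctly detecting drift, not error rates of a rule in the SAP; the SAP nowhere says that app significant and waitlist not significant would count as success. The Mann-Whitney slip is conservative when nothing changes, so it cannot create spurious findings.

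The benign reading does not remove the conflict. 8.2 ties the paired test to the comparison between conditions in so many words and does not mention the interaction for these scores. Its non-parametric fallback also differs from that in SAP 7, so the two sections disagree even if both are about within-group change. A visible waitlist effect size is not a test of the difference.

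**Conclusion.** The concern holds. As written, the 8.2 rule cannot answer the objective it is attached to, and it contradicts SAP 7 and protocol 9.8 with nothing to settle which applies. It should be corrected before analysis.

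The scope is five secondary scores. The primary SQ analysis is unaffected, and so is its per-protocol repeat, which 8.2 models on the primary analysis.

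Under the stated assumptions (no app effect, equal drift, r of 0.3 to 0.7, 150 to 300 per arm), a significant app-arm result appears in 18–61% of trials at 0.1 SD drift, 54–99% at 0.2 SD and 87–100% at 0.3 SD, against about 5% for the between-arm test. The documents give neither the drift nor the correlation, so these ranges only illustrate how uninformative a within-arm p-value is about the app. The case itself rests on the wording and the design. The Mann-Whitney point is minor and touches only supplementary tests.

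**What to change.** In SAP 8.2, replace the sentence naming the paired t-test and Wilcoxon test with the SAP 7 mixed model (group, time, group by time) for each of the five scores. Report the app-minus-waitlist difference in change from baseline at 6 and at 12 weeks with a 95% confidence interval. The minimum needed to remove the contradiction is to point 8.2 to SAP 7; the time-specific differences go a step further but come from the same model. Keep the paired t-test or Wilcoxon signed-rank test only as descriptive within-arm analyses, labelled as such.

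As a minor correction in SAP 7 and protocol 9.8, specify a paired t-test for within-group change and replace Mann-Whitney U with the Wilcoxon signed-rank test.

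The 8.2 change is SAP wording only, since protocol 9.8 already names the interaction as the critical test. Only the minor correction touches protocol text. Neither needs new data or adds participant burden.
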